4.2.4 Secondary endpoint evaluation

The secondary endpoint of superiority for peri-procedural bleeds will be assessed using the same methodology as the primary endpoint, except that the test will be for superiority. If the study does not meet the non-inferiority endpoint, superiority will not be assessed. The overarching goal is to reduce peri-procedural bleeds without causing an increase in stroke. Thrombi may form slowly though clinical presentation may occur months later. Considering events through 6 months post procedure helps to ensure that the interruption of Edoxaban for the procedure does not result in an increase in late-occurring thrombi or other safety issues.

5. Study Population

5.1 Device case mix

The case mix in electrophysiology programs currently is approximately 60% ICD procedures and 40% permanent pacemaker procedures. Of these, new implants constitute approximately 50% and device replacement procedures constitute 50%. Based on the BRUISE control study data, the bleeding rates differ between these groups (de novo implants versus replacement of generator; ICDs versus pacemaker). In addition, significant proportions (20%) of patients have additional lead revision, or lead insertion for device upgrade procedures that can add to the complexity of the procedure and impact the bleed rates. Lead extraction procedures are not permitted in this case mix. The pacemaker component will be capped at 100 subjects and ICD patients at 150 subjects in the first phase of the study. Subjects for potential enrollment in the study will be identified based on their medical and device history, chart review of the outpatient pacemaker clinic or scheduling for device procedures and then undergo evaluation for possible study inclusion criteria and subsequent enrollment.

5.2 Study Inclusion criteria

1. Subjects must be willing and able to give written informed consent
2. Outpatients \geq 18 years of age, male or post-menopausal female patients; premenopausal female patients who are on and will maintain continuous birth control therapy during the study.
3. Subjects must satisfy one of the following four inclusion criteria
 - e) Patients with established AF and bradycardia on long term (>3 weeks) therapeutic OAC with Warfarin or another OAC who are undergoing new pacemaker system implant or existing pacemaker system revision (single chamber, dual chamber or cardiac resynchronization device).

- f) Patients with newly detected bradycardia –tachycardia syndrome and AF who have been recently (less than 3 weeks) started on Warfarin, have a therapeutic INR and no thrombus on trans-esophageal echocardiogram (TEE) who are undergoing a new pacemaker system implant or revision (single chamber, dual chamber or cardiac resynchronization device).
 - g) Patients with AF and ventricular tachyarrhythmias (VT or VF) or acquired structural heart disease who are candidates for ICD therapy and are on long term (>3 weeks) therapeutic OAC with Warfarin or another OAC who are undergoing new ICD system implant or existing ICD system revision (single chamber, dual Chamber or cardiac resynchronization device).
 - h) Patients with newly detected AF with VT or VF who have been recently (less than 3 weeks) started on Warfarin, have a therapeutic INR and no thrombus on TEE who are undergoing ICD system implant or revision (single chamber, dual chamber or cardiac resynchronization device).
- 4. Subjects must be candidates for long-term OAC therapy based on clinical practice guidelines for treatment of NVAf. In subjects on OAC other than Warfarin entering the study, Warfarin therapy must be established with therapeutic INR levels before the procedure.
 - 5. Subjects are candidates for either Warfarin or Edoxaban therapy as per FDA drug approval guidelines. Guidelines for GFR as established for Edoxaban will be applicable to all subjects regardless of randomized drug choice.

5.3 Study Exclusion criteria

- 1. Clinically significant valvular heart disease (defined as atrial fibrillation in a patient with moderate to severe stenosis or regurgitation of one or more cardiac valves and without any other associated comorbidity that can contribute to the development of the arrhythmia).
- 2. Patients requiring CIED lead extraction e.g. for device site infection, endocarditis, leads under advisory or other conditions warranting lead(s) system extraction.
- 3. Recent (<1 month) myocardial infarction
- 4. Documented LA thrombus on TEE
- 5. Contraindications to anticoagulant therapy or adverse event with prior Warfarin or Edoxaban therapy
- 6. Creatinine clearance <30ml/min or >95ml/min
- 7. Advanced hepatic disease

8. Recent stroke (<3 months) or thromboembolic event
9. Recent (<3months) intracranial or other major bleeding event
10. Use of concomitant dual antiplatelet therapy or other oral, subcutaneous or parenteral anticoagulant therapy
11. Patients on Warfarin without therapeutic INR levels before study entry
12. Patients with other clinically significant medical condition
13. Patients with life expectancy < 1 year
14. Lead extraction procedures
15. Premenopausal female patients, who are not on continuous birth control therapy or are likely to discontinue it at any time during the entire duration of study enrollment.
16. Pregnant patients

6. Study Treatments

6.1 Investigational and control drugs

There are only two FDA approved drugs in this study, Edoxaban and Warfarin. No investigational drugs are anticipated.

6.1.1 Run-in Phase

Warfarin may be taken once per day. The allowable doses are 1- 20 mg per day. Subjects should be reminded of dietary and other interactions relevant to Warfarin.

6.1.2 Acute Open Label Phase

Subjects eligible for randomization will have maintained INR values in the therapeutic range based on a patient-specific dose of Warfarin – or baseline Warfarin therapeutic dose. From randomization to assessment of the primary endpoint, the study will be open label in design. In subjects randomized to Edoxaban in accordance with drug labeling, the transition from Warfarin and initiating Edoxaban should be performed when the INR has decreased below 2.5 after the discontinuation of Warfarin.

6.1.3 Follow-up Open Label Phase

[figure not shown]
Subjects randomized to continuous Warfarin should have an INR in the first month, and continue monthly INRs as per standard practice guideline recommendations. Warfarin dosage should be adjusted according to standard practice to keep patients in the therapeutic range. Subjects randomized to Edoxaban should take it once daily per package dosing instructions (Edoxaban 60 mg daily dose for

creatinine clearance 50 to 95 ml/min and Edoxaban 30 mg for creatinine clearance of 30 to 49 ml/min). Subjects will be followed for an additional five months with a phone follow up at 3 months (± 1 week) and final follow up visit at 6 months (± 1 week). After the final follow up visit or after the subject is terminated from the study, subjects on Edoxaban transitioning to Warfarin should be maintained on Edoxaban until the INR is 2.0 or higher before Edoxaban discontinuation in accordance with drug labeling.

7. Study Visits

This study consists of three parts: a run-in or eligibility phase, an acute phase and a follow-up phase. Figure 2 for shows a diagram of study activities. Table 2 and Appendix A show visits.

Figure 2: Study events

Eligibility will be assessed when subjects have completed 3 weeks of Warfarin dosing. The procedure should be scheduled 5 to 15 days after randomization so that subjects are adequately anticoagulated with Warfarin or Edoxaban. The last dose of Edoxaban will be administered less than 24 hours prior to the procedure. Randomization will be obtained via IVRS once eligibility has been confirmed and the procedure has been scheduled.

On the day of the procedure, Warfarin will be continued and Edoxaban will be interrupted. Edoxaban dosing will resume a minimum of 16 and a maximum of 24 hours following the procedure. During and after the procedure, subjects will be assessed for safety and efficacy endpoints for bleeding and

embolism respectively as well as major adverse cardiovascular events (MACE). Edoxaban subjects will in general be discharged on the same day as the procedure, whereas Warfarin subjects will have their discharge timing determined on an individual basis by the investigator.

After discharge, subjects must return to the lab that drew the pre-procedure sample for another blood sample. This post-procedure blood draw should occur 24 to 48 hours after the procedure. The subjects will then resume the standard of care (SOC) follow-up. The SOC includes a pre-discharge visit (4 to 24 hours after procedure), wound care visit (usually 1 to 2 weeks after the procedure) and standard device clinical follow-up procedures. These can include one month, three month or six month visits or remote monitoring as clinically employed in the study.

The primary outcome assessment visit should be 30-days post procedure \pm 3 days. Assessments including focused H&P, concomitant medications, NYHA class, adverse events and hospitalizations will be collected. If a bleeding event has occurred, details including the date, time, required intervention and outcome should be recorded. Documentation of intervention may include the hospital order for vitamin K or blood products.

There will be a telephone follow-up at 3 months after the CIED procedure for MACE and hospitalizations and vital status. The final safety visit should be scheduled 6 months \pm 14-days post procedure or at the time of discontinuation if possible. Assessments including focused H&P, concomitant medications, NYHA class, adverse events and hospitalizations will be collected. If the investigator suspects that a MACE event has occurred, a MACE CRF should be completed.

Table 2: Schedule of study procedures and visits

Time point	Pre-procedure	Procedure (PM or ICD)	Post-procedure					
			Blood Draw	SOC Post Op	1	2	3	
								24-48 h
Demographics								
Medical & AF History	+							
Focused H & P					+			+
Con Meds	+				+			+
NYHA Class	+				+			+
Hemoglobin	+		+					
Procedure Details	PM or ICD							
Adverse Events	+	+		+	+	+	+	+
Hospitalizations	+				+			+

* Phone call

8. Assessment of Safety and Monitoring

Safety monitoring during the study will be performed by medical and clinical monitors and the coordinating center. Sites will be monitored by a clinical monitor at least once during this short trial. At the time of the site visit, the monitors will review implant procedure reports for all cases enrolled. Any issues or problems discovered will be discussed with the investigator; corrective action will be taken as necessary. Any findings will be documented in the monitoring reports and follow-up correspondence.

Clinical sites will be required to report all procedure related complications, deaths and major adverse events (AE) to the medical monitor within 24 hours of learning of the event. The medical monitor will review the case within 24 hours of notification and confer with the local physician as appropriate. The study principal investigator will be notified if the complication is serious or if it appears that the complication or implant failure may have been due to a deficiency of the operator or support facility and personnel. In this case, or if a clinical site reports implant failure or serious complications in conjunction

with two consecutive cases, the clinical site may be suspended from enrolling additional patients until a full examination of the complications and their probable cause can be determined and any problems have been rectified. All adverse events and procedure related complications will be recorded on CRFs and coded using MedDRA and included in tabular reports to the DSMB.

8.1 Adverse events

An adverse event (AE) is the appearance or worsening of any undesirable sign, symptom, or medical condition occurring after randomization, regardless of the relationship to randomized treatment, procedures, underlying disease or comorbidities. All adverse events that occur or worsen after randomization should be reported on the CRF. When possible, the diagnosis or cause of the event should be reported instead of reporting symptoms. When multiple symptoms are related to a cause or diagnosis, only the cause or diagnosis should be reported.

Investigators should follow up with adverse events until they have resolved, the subject dies or withdraws from the study, or until the study is concluded.

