RATIONALE	Perioperative bleeding is a risk of cardiovascular implantable device insertion or replacement procedures. Bleeding complications predispose patients to interruption of OAC therapy, use of reversal agents, infection, and re-operation and prolong hospital stays. In patients with non valvular atrial fibrillation, interrupted Edoxaban therapy may offer safety and efficacy that is non inferior to continuous Warfarin therapy during these procedures
STUDY DESIGN	This is a prospective randomized comparative evaluation of Edoxaban and Warfarin for safety and efficacy in perioperative use in patients with non-valvular atrial fibrillation undergoing clinically indicated implantation or replacement of cardiovascular implantable electrical devices. This study is a randomized, open label, active-controlled trial with an open-label safety extension, designed to compare local and systemic bleeding within 30 days of cardiac rhythm device implant among patients randomized to continuous Warfarin or interrupted (<24 hours) Edoxaban. The study will have three phases; a run in phase to establish stable Warfarin therapy, an acute open label 30-day phase when patients will be randomized in a 1:1 ratio to receive interrupted Edoxaban or continuous Warfarin, which will be followed by an open label follow up phase for an additional 5 months for safety monitoring. Drug transitions will be performed according to approved drug labeling.
PRIMARY OBJECTIVE	The primary objective is to compare the rates of local and systemic bleeding in patients randomized to Edoxaban compared to patients randomized to continuous Warfarin in within 30 days of cardiac rhythm device implant with concomitant non-valvular AF.
SECONDARY OBJECTIVES	The secondary objectives are to compare the rates of thrombotic events (embolism or stroke) and MACE events through 6 months following the procedure in the Edoxaban and Warfarin groups.

NUMBER OF PATIENTS	A maximum of 400 patients will be enrolled

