DURATION OF PATIENT PARTICIPATION AND DURATION OF STUDY	
Screening: 7-26 days
 
Treatment: 5 days of randomized therapy prior to procedure (which is a single day)
 
Follow-up: 180 days

CONCOMITANT MEDICATIONS	Allowed as per approved FDA guidelines
EFFICACY EVALUATIONS	
PRIMARY ENDPOINT	Major local or systemic bleeding as defined in the protocol at 30 days after implant procedure
SECONDARY ENDPOINTS	The secondary objectives are to compare the rates of thrombotic events (embolism or stroke) through 6 months following the procedure in the Edoxaban and Warfarin groups and the rates of MACE events through 6 months following the procedure in the Edoxaban and Warfarin groups
OTHER EVALUATIONS	The exploratory objectives are to compare rates of hemoglobin reductions from pre-procedure to 24-48 hours post procedure in the Edoxaban and Warfarin groups
SAFETY EVALUATIONS	Safety monitoring during the study will be performed by an independent data monitoring committee (DMC), as well as medical and clinical monitors

	and the coordinating center. Sites will be monitored by a clinical monitor at least once during this short trial. Clinical sites will be required to report all procedure related complications, deaths and major adverse events to the medical monitor within 24 hours of learning of the event. All events will be adjudicated by an independent events committee.
PLANNED INTERIM ANALYSES	When approximately 200 subjects have completed the study through the 30-day visit, an interim analysis for safety will be conducted by an independent data monitoring committee. Serious adverse events will be monitored by the committee on an ongoing basis throughout the study. Based on the primary outcome in these 200 subjects, the study may continue to enroll up to 200 additional subjects, or be terminated.
STATISTICS Primary Analysis Plan	This study contains an internal pilot, and the primary endpoint will be evaluated when 200 patients have reached 30-days post procedure or withdrawn. Based on the primary outcome in these 200 patients, the study may enroll up to 200 additional subjects, or be terminated. Bleeding rates will be compared for non-inferiority using a 1-sided exact test (Primary Endpoint). If non-inferiority of Edoxaban is demonstrated, superiority will be assessed using a 2-sided exact test (Secondary Endpoint).

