4.1 Overview

This study is a randomized, open label, active-controlled trial with a safety extension (follow-up phase). It is designed to compare bleeding, local or systemic, within 30 days of cardiac rhythm device implant (acute phase) for non-valvular AF among patients randomized to continuous Warfarin or interrupted

Edoxaban. Randomization will be stratified by device type and HAS-BLED score (≤ 2 or ≥ 3). Patients will be randomized in a 1:1 ratio to receive interrupted Edoxaban or continuous Warfarin. This study contains an internal pilot opportunity to adjust the sample size or terminate the study, and there will be an interim analysis of the primary endpoint when 200 patients have reached 30-days post procedure or withdrawn. Based on the primary outcome in these 200 patients, the study may:

[figure not shown]
- Enroll 200 additional patients (pacemaker capped at 100 patients, ICD capped at 150 patients)
- Enroll 100 additional patients
- Be terminated

The study design is outlined in Figure 1.

Figure 1:

Study Design Flow Chart

Study Timeline

- Seamless design, enrollment does not stop between phases
-  Opportunity to stop if Part I objectives are not met
- Minimal resource commitment to Part II if Part I objectives not met
- For Part II, all sites enrolling, experience should lead to improved data quality compared to Part I
- Phases analyzed separately (primary) and combined

Eligible subjects must be stable on a therapeutic dose of Warfarin (INR 2-3) for three weeks prior to randomization. If potential patients are taking an anticoagulant besides Warfarin, or otherwise not meeting this criteria, must be switched to Warfarin and complete 3 weeks of dosing with INRs in the therapeutic range (run-in period) at randomization.

Comment [s1]: Segment into two sentences.
Insert period

Comment [s2]: delete

Comment [s3]: delete

Comment [s4]: Insert

The final INR should be performed on the day of randomization, and the procedure should be scheduled a minimum of 5 days and at most 15 days after randomization. Once eligibility has been confirmed and informed consent has been obtained, patients will be randomized via an interactive secure web randomization system. Patients will be randomized in a 1:1 ratio to Edoxaban or Warfarin. Randomization will be blocked by HAS-BLED score, and based on a randomization list, which will be created prior to commencement of the study.

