12.2 Informed consent procedures

The investigator or a person designated by the investigator should fully inform the subject of all pertinent aspects of the clinical trial including the written information approved by the local IRB/IEC/REC. Prior to assessment of eligibility, subjects may only be included in the study after providing written, IRB/IEC/REB-approved informed consent. The informed consent must be consistent with local

legal and site requirements, and must be signed and dated by the patient prior to any study-specific procedures occur.

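### Adverse event collection starts at randomization, so a non-fatal bleed or stroke during the protocol-required Warfarin run-in is not a study event and has no defined route to the DMC

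*Combined protocol and SAP*

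**What the plan says.** The synopsis describes three study phases, the first being "a run in phase to establish stable Warfarin therapy". Section 6.1.1 places this phase under study treatments and gives it Warfarin dosing instructions. Under section 4.1, patients taking another anticoagulant, or otherwise short of the INR requirement, "must be switched to Warfarin and complete 3 weeks of dosing with INRs in the therapeutic range (run-in period) at randomization". Section 5.2 makes a similar demand: "In subjects on OAC other than Warfarin entering the study, Warfarin therapy must be established with therapeutic INR levels before the procedure". The synopsis allows for the period with the entry "Screening: 7-26 days".

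Safety collection starts later. Section 8.1 defines an adverse event as one "occurring after randomization, regardless of the relationship to randomized treatment, procedures, underlying disease or comorbidities". It then sets the reporting rule: "All adverse events that occur or worsen after randomization should be reported on the CRF". Section 8.2 defines SAEs as those adverse events that meet a seriousness criterion. Section 10.5 restricts the safety report to patients in whom the implant procedure was begun. On consent, section 12.2 says the form "must be signed and dated by the patient prior to any study-specific procedures occur".

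**The concern.** For a patient who arrives on a different anticoagulant, the run-in is a drug change made because the protocol requires it, followed by three weeks of INR-guided Warfarin, ahead of a device procedure already clinically indicated. Bleeding and thromboembolism are the harms such a change could cause, and they are the harms this trial studies. If the safety rules are followed exactly as written, those harms go uncounted when they occur in the run-in.

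Two things are at stake. The DMC is asked to oversee safety but has no stated means of seeing harm from a study-required treatment change. And readers of the final report could not tell how many patients began the run-in, how many failed it, or why. They would need that to judge how the result applies to people who are on another anticoagulant when a device is planned.

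**Working it through.** The plan states no figure to reproduce; this is a check of one rule against another.

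1. **Is the run-in part of the study?** Yes. The synopsis and section 7 both name it as the first of three parts, section 6.1.1 gives its dosing, and sections 4.1 and 5.2 make the switch mandatory for the patients concerned.

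2. **When does AE collection begin?** Section 8.1 sets randomization as the start twice, once in the definition and once in the CRF rule. Section 8.2 builds SAEs from AEs, so they inherit the same start. No section defines a run-in or pre-randomization event category.

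3. **Could a run-in event be picked up later?** Section 8.1 does include a condition that worsens after randomization, but that needs the patient to be randomized. Section 5.3 excludes a stroke or thromboembolic event (criterion 8) or a major bleed (criterion 9) within the previous 3 months, and an adverse event with prior Warfarin (criterion 5). A patient with a major bleed or stroke in a three-week run-in would therefore become ineligible, would not enter the intention-to-treat set, and would not have the implant started within the trial. Section 10.5 then leaves that patient out of the safety report. No section asks for a log of run-in failures.

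4. **What reaches the DMC?** The stated inputs are tabulated adverse events and procedure complications (section 8), ongoing review of SAEs (synopsis), and serious implant complications (section 9.2). A run-in bleed or stroke is none of these.

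5. **Scale in time.** Inputs: run-in 21 days (3 weeks, section 4.1); randomization to procedure 5 to 15 days (sections 4.1 and 7); primary endpoint at 30 days; follow-up 180 days (synopsis). Share of time before AE collection = 21 / (21 + days to procedure + follow-up days).
   - To the 30-day endpoint: 21/(21+5+30) = 21/56 = 37.5%; 21/(21+15+30) = 21/66 = 31.8%.
   - To the final visit: 21/(21+5+180) = 21/206 = 10.2%; 21/(21+15+180) = 21/216 = 9.7%.

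   Section 8.1 covers none of the 21 days. The 7-day lower limit on screening cannot hold a three-week run-in, so it can apply only to patients who do not need one.

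6. **A related inconsistency.** Section 10.5 puts randomization on the procedure day, whereas sections 4.1 and 7 put it 5 to 15 days earlier. If section 10.5 were followed, the uncollected period would run up to the procedure. These passages must be reconciled.

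**The case against.** Several points can fairly be made for the plan.

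- **The visit tables.** Table 2 and Appendix A mark adverse events and hospitalizations in the Pre-procedure column. That is the only column before the procedure, and it also holds history, NYHA class and baseline hemoglobin, so it could be read as covering screening. It could equally mean the 5 to 15 days after randomization. A mark in a schedule does not override the explicit definition in section 8.1. The ambiguity stands and needs settling.
- **Deaths.** The 24-hour rule in section 8 names deaths as a separate item and gives no start date, so it would be wrong to infer that run-in deaths go unreported. They may well reach the medical monitor. The same sentence is weaker for non-fatal events, because it relies on the AE term that section 8.1 limits.
- **Monitoring.** A reader might infer that run-in patients are unobserved. They are not: INRs must be in range. What is missing is a rule for reporting events.
- **Selection.** A reader might infer that the run-in enriches the Warfarin arm for tolerance. Selection happens before randomization, so it applies to both arms, and section 5.3 makes it openly part of eligibility. Collecting run-in events would describe this selection, not remove it.
- **Consent.** It is tempting to say that run-in patients have already consented. Section 12.2 puts consent before eligibility assessment and study-specific procedures, but section 7 assesses eligibility after the three weeks, and section 4.1 mentions consent just before randomization. Whether the switch counts as a study-specific procedure is not stated.
- **Documents not available.** The DMC charter and Data Management Plan are separate and might add a rule. Nothing in the protocol says that they cover the run-in.

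These points narrow the concern; they do not supply a reporting route for a non-fatal run-in bleed or stroke.

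**Conclusion.** The point holds as a gap in safety reporting. Under sections 8.1, 8.2 and 10.5 as written, a non-fatal major bleed or stroke during the required run-in is neither an AE nor an SAE, is absent from the safety report, and has no defined path to the DMC. A run-in death may be notified under section 8 but is likewise outside both definitions.

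A reader might go further and infer a biased bleeding comparison or an affected type I error. The documents do not support that: these events precede randomization, and the primary analysis concerns randomized patients only.

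The size can be stated only as time, a 21-day period for each patient who completes the full run-in. The number of patients or events cannot be estimated, because the documents give neither the share entering on another anticoagulant nor an event rate for the run-in. The conclusion assumes that section 8.1 governs over the visit tables and that no separate document extends collection backward.

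**What to change.** - In sections 8.1 and 8.2, start collection of SAEs, deaths, bleeding and thromboembolic events at the first protocol-directed Warfarin dose, for every patient who enters the run-in.
- In section 12.2, state that consent precedes the switch to Warfarin. Without this, a collection rule tied to consent might miss the run-in altogether.
- Give the DMC these events as a separate pre-randomization listing.
- Log every patient who starts the run-in but is not randomized, with the reason, and account for them in the final report.
- Reconcile the Pre-procedure column in Table 2 and Appendix A, and both the safety population and the randomization day in section 10.5, with the above.
- Keep the randomized comparison starting at randomization, so the primary analysis does not change.

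The cost is a few sentences of text and earlier use of the existing SAE forms. The downside is modestly more SAE reporting, including for patients who are never randomized.
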